5.2.2 Informed Consent

The Investigator or his/her authorized designee (if applicable) will conduct the Informed Consent process, as required by applicable regulations and the center's IRB/EC. This process will include a verbal discussion with the patient on all aspects of the study that are relevant to the patient's decision to participate, such as details of study procedures, anticipated benefits, and potential risks of study participation. Sites must inform patients about their right to withdraw from the study at any time and for any reason without sanction, penalty, or loss of benefits to which the patient is otherwise entitled. Withdrawal from the study will not jeopardize their future medical care or relationship with the investigator.

During the discussion, the Principal Investigator or his/her authorized designee will avoid any improper influence on the patient and will respect patient's legal rights. Financial incentives will not be given to patients. Patients may be compensated for time and travel directly related to the participation in the study. The site shall provide the patient with the Informed Consent form written in a language that is understandable to the patient and that has been approved by the center's IRB/EC. The patient shall have adequate time to review, ask questions, and consider participation. The Principal Investigator or his/her authorized designee will make efforts to ensure that the patient understands the information provided. If the patient agrees to participate, they must sign and date the Informed Consent form, along with the person obtaining the consent prior to any study-specific procedures. The site will file the signed original in the patient's hospital or research charts and provide a copy to the patient.

Sites should report any failure to obtain informed consent from a patient to the Sponsor within 5 working days and to the reviewing center's IRB/EC according to the IRB's/ EC's reporting requirements.

If, during the study, new information becomes available that can significantly affect a subject's future health and medical care, the Principal Investigator or his/her authorized designee (if applicable) will provide this information to the subject. If relevant, sites will ask the subject to confirm their continuing informed consent in writing.

5.2.2.1 Special Circumstances for Informed Consent

Sites may enroll individuals who are unable to make the decision to participate in a study on their own. Sites will obtain informed consent from the patient's legally authorized representative and will inform the patient about the study within his/her ability to understand. During the informed consent discussion, the Principal Investigator or his/her authorized designee will avoid any improper influence and make sure there is no manipulation of the patient and patient's legal rights are respected. Enrollment of these patients is important as data of comparable validity cannot be obtained from clinical research involving persons able to give informed consent or by other research methods. -

The legally authorized representative will represent the individual during the Informed Consent process, which will be performed according to the requirements in **Section 5.2.2**. Sites will respect the explicit wish of the individual to decline participation or withdraw from the study at any time. In addition, no incentives or financial inducements will be provided to these patients or their legally authorized representatives for their participation in the study.

This study excludes individuals under the age of 18.

Sites may enroll individuals unable to read or write in this study. Sites will obtain informed consent through a supervised oral process. An independent witness will be present throughout the Informed Consent process. A member of the site's study team previously trained to the CIP will read the written Informed Consent form and any other information aloud and explain to the prospective subject or his/her legally acceptable representative and will sign and personally date the Informed Consent form. The witness will also sign and personally date the Informed Consent form attesting that the information was accurately explained, and that informed consent was freely given. In addition, no incentives or financial inducements will be provided to these patients or their legally authorized representatives for their participation in the study.

Sites may enroll women who are pregnant or breastfeeding in this study. Informed consent must be obtained using the IRB/EC approved informed consent in accordance with IRB/EC requirements. The study is expected to produce a direct benefit to the woman or her embryo, fetus, or child, outweighing the risks and burdens involved. When breastfeeding women are included, care shall be taken to avoid any adverse impact to the health of the child. In addition, no incentives or financial inducements will be provided to these patients or their legally authorized representatives for their participation in the study. All other aspects of the Informed Consent process will follow **Section 5.2.2**.

Sites may enroll individuals admitted to the emergency units in this study in cases where emergent removal of life- or limb-threatening thrombi in the peripheral vasculature is required. When prior informed consent of the individual is not possible because of the patient's medical condition, sites will request the informed consent of the subject's legally acceptable representative, if present. When it is not possible to obtain prior informed consent from the subject, and the subject's legally acceptable representative is not available, sites will perform the informed consent process in accordance with **Section 5.2.2** as soon as possible. In addition, patients are able to enroll in the study post-procedure.

For live cases at congresses, the subject needs to sign a specific Live Case ICF, approved by the IRB/EC. The investigator must notify the Sponsor prior to performing a live case.

5.3 Eligibility Criteria

5.3.1 General Eligibility Criteria

Assessment for general eligibility criteria is based on medical records of the site and interview with a candidate patient. Patients must meet ALL general inclusion criteria to participate in the study. If ANY general exclusion criteria are met, the patient is excluded from the study and cannot be enrolled (recruitment failure).

5.3.2 Inclusion Criteria

5.3.2.1 General Inclusion Criteria

1. Subject was treated or is expected to be treated for acute/subacute thrombosis, as determined by investigator, in the peripheral vasculature with the JETi Hydrodynamic Thrombectomy System.
2. Subject or legally authorized representative must provide written informed consent
3. Subject must be ≥ 18 years of age and of Asian race.

5.3.3 Exclusion Criteria

5.3.3.1 General Exclusion Criteria

1. Subject has previously been registered in the JETi Hong Kong PMS in the last 12 months unless treated in the contralateral limb/different anatomy; patients treated in the contralateral limb/different anatomy within the last 12 months may re-enroll in the study.
2. Subject is currently participating in another drug or device clinical investigation.
3. Subject has active symptoms and/or a positive test result of COVID-19 or other rapidly spreading infectious agent within the past 20 days.

5.4 Subject Enrollment

A patient is considered enrolled in the study from the moment the patient provides written informed consent.

5.5 Subject Registration

An enrolled subject is considered registered in the study only after a JETi Catheter is introduced into the intended vasculature of the subject during the procedure (Day 0). Patients may be consented after the procedure if all assessments needed for the primary endpoints are complete. A subject who is enrolled but not registered in this study will be considered a screen failure. The sample size of the study is based on the number of registered subjects.

5.6 Subject Withdrawal and Discontinuation

Each registered subject shall remain in the study until completion of the required follow-up period; however, a subject's participation in any study is voluntary, and the subject has the right to withdraw at

any time without penalty or loss of benefit. Conceivable reasons for discontinuation may include, but not be limited to, the following:

- Subject death
- Subject voluntary withdrawal
- Subject lost-to follow-up as described below
- Subject's follow-up is terminated according to **Section 3.3**.

Sites must notify the Sponsor of the reason(s) for subject discontinuation. Investigators must also report this to their respective IRB/EC as defined by their institution's procedure(s).

No additional follow-up is required, or data recorded from subjects once withdrawn from the study, except for the status (deceased/alive).

However, if a subject withdraws from the study due to problems related to the safety or performance of the JETi System, the investigator shall ask for the subject's permission to follow his/her status/condition outside of the study.

In case of subject withdrawal of consent, the site should make attempts to schedule the subject for a final study visit. At this final follow-up visit, the subject will undergo clinical assessment.

Lost-to-Follow-up

If the subject misses the 30-day follow-up time point and the attempts at contacting the subject detailed below are unsuccessful, then the subject is considered lost-to-follow-up. Site personnel shall make all reasonable efforts to locate and communicate with the subject (and document these efforts in the source documents), including the following, at each contact time point:

- A minimum of two telephone calls on different days over the specified follow-up windows to contact the subject should be recorded in the source documentation, including date, time and initials of site personnel trying to make contact.
- If these attempts are unsuccessful, the site should send a letter (certified if applicable) to the subject.
- If a subject misses the 30-day follow up timepoint and the above-mentioned attempts at communicating with the subject are unsuccessful, the subject will be considered lost-to-follow-up.

Note: Telephone contact with General Practitioner, non-study cardiologist or relative without the presence of the subject or indirect documentation obtained via discharge letters will not be considered as subject contact.

5.7 Number of Subjects

The study will register approximately 20 subjects.

5.8 Total Expected Duration of the Clinical Investigation

[REDACTED] The expected duration of each subject's participation is 30 days (in cases of prospective consent). [REDACTED]

[REDACTED] Subjects will exit the study at the end of their 30-day Follow-Up visit or 30 days after their procedure. [REDACTED]

6 TREATMENT AND EVALUATION OF ENDPOINTS

For this study, the following definitions apply:

- **Index procedure:** the entire intervention to treat the subject's peripheral vascular thrombosis. A subject's procedure may include more than one session if the subject is removed from the interventional suite and placed in a holding area with the intention of returning to the suite for additional treatments either the same day or following day (e.g., catheter placement or removal for CDT).
- **Treatment:** the individual techniques performed during a procedure to address the subject's peripheral vascular thrombosis (e.g., JETi thrombectomy, balloon angioplasty, stent placement, or catheter-directed thrombolysis (CDT)). Note that "JETi treatment" will refer to treatment during which the JETi Thrombectomy system is used.

NOTE: A subject's treatment is determined by the treating physician based on the clinical situation and institutional practices.

- **Session:** a session is the in and out period within an interventional suite that a subject is receiving treatment. A subject's procedure may include more than one session if the subject is removed from the interventional suite and placed in a holding area with the intention of returning to the suite for additional treatments either the same day or following day (e.g., catheter placement or removal for CDT).

NOTE: Treatment for unexpected re-thrombosis is an adverse event and should not be considered as an additional session of the initial procedure. Refer to **Section 7.1.1**.

6.1 Arterial and Arteriovenous Subjects

At Baseline, demographic information, medications, clinical assessment, physical exam and a medical history will be collected. Laboratory assessments, up to 14 days prior to the procedure, will be recorded and may include estimated glomerular filtration rate (eGFR), serum creatinine (SCr), blood urea nitrogen (BUN), potassium (K), hemoglobin (Hgb), platelets (plt), prothrombin time (PT), international normalized ratio (INR) and activated partial thromboplastin time (aPTT).

The pre-JETi angiogram will be used to assess the initial degree of clot burden after catheter insertion into the vessel and prior to JETi Thrombectomy. The post-JETi Thrombectomy angiogram will be used to assess clot removal after JETi Thrombectomy and prior to any adjunctive therapies used to treat underlying culprit lesions. The final angiogram will be completed to assess clot removal after JETi Thrombectomy and any/all adjunctive therapies and prior to removal of the vascular sheath. All treated

vessels will be assessed using the provided clot removal grades (**Table 1**). All angiograms are requested to be transmitted to the core lab for analysis. Guidance from the imaging core laboratory will be provided for reference.

DUS will be collected at baseline and 30-Day Follow-Up for subjects with arteriovenous thrombosis. Refer to the DUS core laboratory guidelines for detailed information. All DUS completed are requested to be transmitted to the core lab for analysis.

An ABI examination is required at Baseline and 30 Days. Rutherford classification is required at Baseline and 30 Days. Note: baseline ABI (within 3 months prior to procedure) and Rutherford assessment (within 4 days prior to procedure) can be obtained via a non-study physician, including a referring physician; this will not be considered a protocol deviation. Note these are applicable to lower extremity arterial subjects only.

The Short Form (SF)-12 is a self-reported outcome quality of life measure. Its completion is requested at Baseline and at 30 days. For post-procedurally consented subjects, a baseline SF-12 will not be collected as the validity of this assessment is not supported when collected retrospectively.

Anticoagulants, and antiplatelet medications will be collected for this study at Baseline (medications that the patient was taking within the 30 days prior to admission and upon admission), Index Procedure, Discharge, and 30-day follow-up timepoint. Thrombolytics used during the index procedure will be collected.

AEs experienced by the patient during the study will be reported, starting as soon as the JETi catheter is introduced into the intended vasculature during the procedure. Please refer to AE reporting section 7.3.1 for additional details of event reporting.

The schedule of events for arterial subjects is located in **Section 6.1.6**

Data collection at each timepoint is discussed in the sections below.

6.1.1 Baseline

Subject preparation will occur in accordance with standard hospital policy for the care of interventional endovascular procedures. Note that no data will be recorded until consent is obtained. The following baseline data will be collected:

- Enrollment
- Demographics – including age, sex
- Medical history – subject medical history including general medical history, surgical history, vascular history, renal history, and thrombotic condition
- Medications: anticoagulant, antiplatelet, and thrombolytic medications (if applicable) taken within the 30 days prior to admission
- Laboratory assessments (within 14 days prior to the JETi procedure) such as:
 - eGFR

- Serum Creatinine (SCr)
- Blood urea nitrogen (BUN)
- Potassium (K)
- Hemoglobin (Hgb)
- Platelets (Plt)
- International normalized ratio (INR)
- Prothrombin time (PT)
- Activated partial thromboplastin time (aPTT)
- Clinical assessment (within 14 days prior to the JETi procedure) – clinical assessment information including height, weight, blood pressure, heart rate, temperature, and respiratory rate
- Physical exam (within 14 days prior to the index procedure)
- Quality of life (QOL) questionnaire: SF-12 (not applicable for post-procedure consented subjects)
- ABI
- Rutherford classification *

** Note: ABI (done within 3 months prior to procedure) and Rutherford assessment (done within 4 days prior to procedure) can be obtained via a non-study physician, including a referring physician; this will not be considered a protocol deviation. ABI and Rutherford are applicable to lower extremity arterial subjects only.*

- Duplex ultrasound examination will be collected at Baseline (up to 14 days prior to the index procedure) for arteriovenous subjects. Guidance from the imaging core laboratory will be provided for reference. All DUS completed are requested to be transmitted to the core lab for analysis.

6.1.2 Index Procedure

The thrombectomy procedure with the JETi System should be conducted in accordance with standard of care practice and approved labelling. All consented subjects who have the JETi Catheter introduced into the intended vasculature will be considered registered subjects and will be entered into the study.

The following procedural data will be collected:

- **Procedure information:** Start and end dates/times, amount of contrast used during the entire procedure, total fluoroscopy time, access sites, obstruction location, and the number of sessions within the procedure (If multiple sessions were needed, the location of the subject in between the sessions is requested).
- **Treatment information:** The treatments performed during the index procedure will be captured in the order of performance with specific details for each treatment. The treatment options will include the following:
 - JETi mechanical thrombectomy (MT) only
 - JETi in combination with one or more of the following treatments:

- **Imaging Assessments:**

- Pre-JETi arteriogram: The pre-JETi arteriogram will be used to assess the initial degree of clot burden after catheter insertion into the vascular system and prior to JETi thrombectomy.
- Post-JETi arteriogram: The post-JETi thrombectomy arteriogram will be used to assess the degree of clot removal after JETi thrombectomy and prior to any adjunctive therapies used to treat underlying culprit lesions.
- Final arteriogram: The final angiogram will be completed to assess the degree of clot removal after JETi thrombectomy and any/all adjunctive therapies and prior to removal of the vascular sheath.

All treated vessels will be assessed using the provided grades in Table 1, per core lab assessment.

All treated arterial vessels will be assessed using the provided TIPI grades in Table 3, per core lab assessment.

- **Acute success**, as per [REDACTED] (**Table 3**), per core lab assessment:

- Device success: Near complete or complete recanalization of occluded vessel, defined as post-JETi [REDACTED]
- Technical success: Near complete or complete recanalization of occluded vessel, defined as [REDACTED] where [REDACTED] evaluation occurs after JETi system and any other adjunctive device or procedures (final).
- Procedural success: Technical success with no JETi-related MAEs within 5 days of registration or by discharge, whichever occurs first.

- **Adverse Events and Device Deficiency assessment**

- **Medications:** Anticoagulant, antiplatelet, and thrombolytic medications administered during the procedure; anticoagulant and antiplatelet treatments within the peri-operative period should follow recommended societal guidelines.

6.1.3 Discharge

Discharge is defined as the subject leaving the treating hospital. The following discharge data will be collected:

- Adverse events and device deficiency
- Medications: Anticoagulant, and antiplatelet medications

6.1.4 30-day Follow-up (Office Visit)

A 7-day window is required for the 30-day follow-up visit (30 days \pm 7 days). The following data will be collected at the follow-up visit:

- Adverse events and device deficiency
- Medications: Anticoagulant, and antiplatelet medications
- ABI*
- Rutherford classification*

* Note: ABI and Rutherford assessment can be obtained via a non-study physician, including a referring physician; this will not be considered a protocol deviation. ABI and Rutherford are only applicable to lower limb arterial thrombosis.

- QOL questionnaire (SF-12)
- Duplex ultrasound examination will be collected at 30 days for arteriovenous subjects. Guidance from the imaging core laboratory will be provided for reference. All DUS completed are requested to be transmitted to the core lab for analysis.

6.1.5 Unscheduled Visit

Unscheduled visits may occur as clinically warranted, and data will be collected if the unscheduled visit is related to the JETi procedure and/or investigational device (as determined by the physician). Data on any imaging, clinical assessment, medication (anticoagulant, antiplatelet, and thrombolytic medications), AEs, DDs and SAEs will be collected if applicable.

6.1.6 Schedule of Events

The schedule of assessments for Arterial Subjects is listed in **Table 4**.

Table 5. Assessment Schedule for Arterial and Arteriovenous Subjects

CIP Activity	Baseline	Index Procedure	Discharge	30 Days Follow-up ¹ (± 7 days)	Unscheduled Visit
Enrollment ²	X				
Demographics	X				
Medical history	X				
Medications	X	X	X	X	X ³
Laboratory assessments					
eGFR	X ⁴				
Serum Creatinine (SCr)	X ⁴				
Blood Urea Nitrogen (BUN)	X ⁴				
Potassium (K)	X ⁴				
Hemoglobin (Hgb)	X ⁴				
Platelets (Plt)	X ⁴				
International Normalized Ratio (INR)	X ⁴				
Prothrombin Time (PT)	X ⁴				
Activated Partial Thromboplastin Time (aPTT)	X ⁴				
Clinical assessment	X ⁴				
Physical exam	X ⁴				
ABI	X ^{5, 6}			X ⁶	
Rutherford classification	X ^{6, 7}			X ⁶	
Imaging assessment – Angiogram		X ⁸			
Imaging assessment – DUS	X ⁹			X ⁹	
QOL (SF-12)	X ¹⁰			X	
Adverse event assessment/Device Deficiency assessment		X ¹¹	X ¹¹	X ¹¹	X ¹¹
Procedure, treatment information		X			

¹ in-office visit is required at 30-day follow-up. A telephone contact or virtual visit is an option only for subject who would otherwise miss the visit due to being unable to complete an office visit

² retrospective consent is permitted

³ unscheduled medications reported in Adverse Event form when applicable

⁴ assessment done within 14 days prior to procedure is acceptable

⁵ ABI done within 3 months prior to procedure is acceptable. In emergent ALI cases, missing ABI at baseline will not be considered a protocol deviation

⁶ can be obtained via a non-study physician, including a referring physician; this will not be considered a protocol deviation

⁷ Rutherford classification done within 4 days prior to JETi procedure is acceptable

⁸ includes pre-JETi, post-JETi, and final (after JETi and all adjunctive device/treatment) angiograms

⁹ only applicable for arteriovenous thrombosis

¹⁰ not applicable for post-procedure consented subjects

¹¹ Serious adverse events (SAEs) and device deficiencies must be reported within 3 calendar days of Site becoming aware

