For this study, the definition of Lower Extremity Deep Vein Thrombosis will apply to lower extremity venous thrombosis involving the femoral, common femoral, or iliac veins, or popliteal, or inferior vena cava (IVC) alone or in combination.

Acute clot for this study is defined based on signs and symptoms of onset of <2 weeks

Subacute clot for this study is defined based on signs and symptoms of onset of 2-6 weeks

Chronic clot for this study is defined based on signs and symptoms of onset of >6 weeks.

Major Bleeding (per BARC)

- BARC 3a: Overt bleeding plus hemoglobin drop of 3 to < 5 g/dL (provided hemoglobin drop is related to bleed); transfusion with overt bleeding or
- BARC 3b: Overt bleeding plus hemoglobin drop \geq 5 g/dL (provided hemoglobin drop is related to bleed); cardiac tamponade; bleeding requiring surgical intervention for control; bleeding requiring IV vasoactive agents or
- BARC 5a Probable fatal bleeding; no autopsy or imaging confirmation but clinically suspicious or
- BARC 5b Definite fatal bleeding; overt bleeding or autopsy, or imaging confirmation

Pulmonary Embolism (per AHA)

Low-risk Pulmonary Embolism: Acute PE and the absence of the clinical markers of adverse prognosis that define massive or submassive PE

Massive Pulmonary Embolism: Acute PE with sustained hypotension (systolic blood pressure <90 mm Hg for at least 15 minutes or requiring inotropic support, not due to a cause other than PE, such as arrhythmia, hypovolemia, sepsis, or left ventricular [LV] dysfunction), pulselessness, or persistent profound bradycardia (heart rate <40 bpm with signs or symptoms of shock).

Sub-massive Pulmonary Embolism: Acute PE without systemic hypotension (systolic blood pressure \geq 90 mm Hg) but with either RV dysfunction or myocardial necrosis.

- RV dysfunction means the presence of at least 1 of the following:
 - RV dilation (apical 4-chamber RV diameter divided by LV diameter >0.9) or RV systolic dysfunction on echocardiography
 - RV dilation (4-chamber RV diameter divided by LV diameter >0.9) on CT
 - Elevation of BNP (>90 pg/mL)
 - Elevation of N-terminal pro-BNP (>500 pg/mL); or
 - Electrocardiographic changes (new complete or incomplete right bundle-branch block, anteroseptal ST elevation or depression, or anteroseptal T-wave inversion)
- Myocardial necrosis is defined as either of the following:
 - Elevation of troponin I (>0.4 ng/mL) or
 - Elevation of troponin T (>0.1 ng/mL)

Renal Failure

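### A baseline ABI up to 3 months old is accepted without having to follow onset of the treated thrombosis, so the baseline/30-day ABI comparison can include pre-occlusion values

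*Combined protocol and SAP*

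**What the plan says.** Section 4.2.2 lists the ABI of the treated limb, at baseline and 30 days, as a descriptive endpoint for lower-extremity arterial subjects. Rutherford class is listed at the same two times for the same subjects.

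On timing, the plan is consistent in three places:

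- Section 6.1 states "An ABI examination is required at Baseline and 30 Days". It then allows "baseline ABI (within 3 months prior to procedure) and Rutherford assessment (within 4 days prior to procedure") to come from a physician outside the study.
- Section 6.1.1 repeats the windows: "ABI (done within 3 months prior to procedure) and Rutherford assessment (done within 4 days prior to procedure").
- Table 5 in Section 6.1.6 has "ABI done within 3 months prior to procedure is acceptable" in footnote 5 and "Rutherford classification done within 4 days prior to JETi procedure is acceptable" in footnote 7. Footnote 5 adds: "In emergent ALI cases, missing ABI at baseline will not be considered a protocol deviation".

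The population is set in Section 5.3.2.1: "Subject was treated or is expected to be treated for acute/subacute thrombosis, as determined by investigator, in the peripheral vasculature". Appendix II, within its deep vein thrombosis entry, says "Acute clot for this study is defined based on signs and symptoms of onset of <2 weeks" and puts subacute clot at 2 to 6 weeks.

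Section 4 rules out hypothesis testing. Section 8.2 plans counts, percentages and the usual summary statistics, and Section 8.8 analyses available data only.

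**The concern.** A baseline is useful in a before-and-after summary only if it describes the limb that was treated. The ABI window is long compared with the duration of an acute or subacute thrombosis, and nothing ties the measurement to onset. A value taken before the vessel occluded therefore meets the rule as written.

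Old chart values are a foreseeable source, although the documents give no frequency. Baseline ABI may come from a referring physician. Consent may be given after the procedure if the assessments for the primary endpoints are complete (Sections 3.1 and 5.5). ABI is not one of those, and once the procedure is over only an existing measurement can serve as its baseline. Footnote 5 deals with a missing ABI in emergent limb ischemia but says nothing about an old one.

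At stake is how the ABI summary is read. A limb with a pre-occlusion baseline can return to its former state by 30 days and show little or no gain, although its perfusion improved from the occluded state.

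**Working it through.** The plan states no figure for this point, so there is none to reproduce. The check has two parts: dates and direction.

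**Dates.** Let *a* be the days from ABI to procedure, *t* the days from onset to procedure, and *W* the accepted window. An ABI is accepted if *a* ≤ *W*, and pre-dates onset if *a* > *t*. An accepted pre-onset value is therefore possible whenever *t* < *W*, and the stretch of window before onset is max(0, *W* − *t*).

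Inputs:

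- ABI window of 3 months (Sections 6.1, 6.1.1, 6.1.6): *W* = 3 × 365.25/12 = 91.3 days.
- Rutherford window (same sections): *W* = 4 days.
- Onset at 14 and 42 days: the 2-week and 6-week limits in Appendix II. Onset at 1 day is an assumed example.

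| Onset before procedure | ABI: accepted days before onset | Rutherford: accepted days before onset |
|---|---|---|
| 1 day | 91.3 − 1 = 90.3 | 4 − 1 = 3 |
| 14 days | 91.3 − 14 = 77.3 | 0 |
| 42 days | 91.3 − 42 = 49.3 | 0 |

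Under the Appendix II limits, any ABI more than 42 days old pre-dates onset in every acute or subacute subject. Rutherford class has the same gap only when onset is less than 4 days before the procedure. The table gives lengths of permitted window. It says nothing about how many subjects have an old value.

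**Direction.** The comparison of interest is ABI(30 days) − ABI(occluded). With a pre-onset baseline, what is recorded is ABI(30 days) − ABI(pre-onset). The recorded gain is smaller by

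ABI(pre-onset) − ABI(occluded).

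This is generally positive, because occlusion lowers ankle pressure. It is smaller where the limb was already ischemic; Section 4.1.1 allows subjects with chronic limb ischemia or peripheral artery disease. Averaged over subjects with both values, the understatement is *p* × *d*, where *p* is the share of baselines taken before onset and *d* is the mean fall at occlusion in those subjects. The documents give neither *p* nor *d*, nor the number of lower-extremity arterial subjects among the approximately 20 planned. If *p* or *d* is zero, so is the effect. I put in no trial values, because the answer would only return the assumption.

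**The case against.** The strongest reply is that the window is a deliberate, practical choice. This is a small real-world study under local practice. The sponsor plainly considered ABI timing, since the same footnote covers emergent cases, and chose completeness over recency. The endpoint is descriptive and no change score or paired display is specified. The case report forms are under separate cover and may already hold both dates: a 3-month limit is hard to verify without the ABI date, and Section 6.1.1 collects the thrombotic condition. Parts of Sections 8.5 to 8.7 are not visible, so a relevant display may exist there.

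Most of this stands, and it limits the point to a low priority. It does not remove it. Two summaries of one measure at baseline and 30 days invite comparison, and no visible rule separates baselines that describe the treated state from those that do not.

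A reader might infer more than the documents support:

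- *That most subjects have a pre-onset ABI.* The 77.3 and 49.3 days are 85% and 54% of the window, but these are calendar fractions and not shares of subjects. The Appendix II limits also sit in the deep vein thrombosis entry, although worded as applying to the study, and eligibility rests on the investigator's judgement. The finding does not need those limits: any onset less than 3 months old leaves a gap.
- *That post-onset values should become the main baseline.* In a very small subset this would leave few values, selected toward subjects stable enough to be measured before the procedure. It is a debatable trade-off, not a correction.
- *That sites need protection from a deviation.* An ABI within 3 months is already acceptable, so a pre-onset value inside the window is not a deviation.

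**Conclusion.** The point holds in a limited form. As written, the rule lets a baseline ABI pre-date the occlusion that was treated. Where that happens, comparing the baseline and 30-day ABI summaries would tend to understate improvement.

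The direction rests on one assumption, that ABI before occlusion is generally higher than during it. This is a tendency: progression of chronic disease or an intervening procedure could alter it in an individual. The size is unknown and may be zero. The effect is confined to a descriptive, non-primary endpoint in the lower-extremity arterial subset. Clot removal grade and the composite of device-related major adverse events do not use ABI and are unaffected. This is a cheap improvement of low priority.

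**What to change.** Keep the 3-month window, and:

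1. Capture the ABI date and the onset date of the index symptoms, if the case report forms do not already do so.
2. Flag each baseline ABI as pre- or post-onset.
3. Report the baseline and 30-day ABI summaries twice, once with all accepted values and once restricted to subjects with a post-onset baseline, with the number of subjects in each.
4. Apply the same flag to Rutherford class when onset is less than 4 days before the procedure.

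The cost is up to two date fields, one flag and one extra display. No accepted value is discarded, no test is added, and eligibility and care do not change. The downside is that the post-onset subset will be small and may favour subjects stable enough to have an ABI measured before the procedure. Showing both summaries with their numbers lets the reader see this.
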